This parametric comparative trial will randomly assign 140 inner-city adolescents with ADHD to (1) CASH-AA Only or (2) CASH-AA + MIP. Treatment will occur in community behavioral health clinics. All participants will receive behavioral interventions (CASH-AA): family psychoeducation in ADHD symptoms, executive functioning, and developmental impacts; family-based motivation and ADHD accommodation interventions; and academic training focused on home environment support and organizational skills. Half of the participants

will also receive medication decision-making interventions (MIP): ADHD medication psychoeducation, family decision-making interventions, and (for those who elect to start medication) coordinated medication management. Half of the sample will have comorbid substance use problems. Treatment will occur in three community clinics; therapists will be randomly assigned to study condition. Caregivers and adolescents will complete assessments at baseline, 3, 6, and 12-month follow-up. Multilevel modeling will compare the effectiveness of each condition on key patient and service use outcomes. Patient-centered analyses will explore differential treatment effects based on (a) Medication decision (yes/no); (b) Substance use comorbidity (yes/no); (c) Race/Ethnicity (Hispanic, African American).

Quantitative outcome analyses will test for service use effects, symptom reduction, and quality of life improvements that are primary reasons for seeking clinical services. Qualitative interviews will document family-specific rationale for decisions about medication, compliance with behavioral and medication interventions, and suggestions for improving services and service integration. Note that families assigned to CASH-AA Only will retain the option of pursuing ADHD medication through treatment-as-usual procedures at their respective clinic. Similarly, families assigned to CASH-AA + MIP will not be required to start ADHD medication. Instead, they will receive informed-choice interventions and can choose when and if to start medication; the study will assess the impact of these decisions on clinical outcomes.

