intensive family engagement and family-agency coordination efforts to help families overcome barriers to enrolling in services, procedures especially valuable for enrolling hard-to-engage families. Linking procedures will cease upon completion of the first intake interview (after which randomization will occur). After linking is completed, research staff will maintain contact with families solely to complete follow-up interviews, which will occur with every randomized family regardless of treatment attendance.

Randomization to study condition and therapist assignment. Cases will be randomly assigned to study condition after completing an intake interview at the assigned site. Urn randomization will promote balance between conditions on 3 variables: sex, ethnicity (Hispanic, African-American, Other), and ASU problems (Yes, No). Once randomized, cases will be assigned to a study therapist in alternate turns. Note that in some sites, it will be necessary to follow “nearly random” assignment to condition, if the given site assigns cases to clinicians based on a shared rotation of case assignment. That is: Any given case is assigned to the next available clinician in the duty rotation, or, the clinician who is on duty during the given intake appointment. Treatment site therapists who agree to participate as study therapists will be consented in their private offices by research staff. We anticipate some degree of therapist dropout due to staff turnover during two years of enrolling study cases. When a study therapist drops out in either condition, the given site will be asked to nominate two potential replacements, and the new therapist will be randomly selected from that pair. All partnering treatment sites will be in close proximity to assigned study participants and easily accessible via public transportation. Each site will routinely prescribe weekly treatment sessions and offer in-house psychiatric support for all cases. All therapists at each site who treat adolescent clients and who volunteer to participate will be accepted into the study randomization pool.

Study Conditions

Behavioral Only Condition: Changing Academic Support in the Home for Adolescents with ADHD (CASH-AA)

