Study therapists will be asked to provide four kinds of study data: (1) Upon consenting to participate in the study, therapists will complete one questionnaire documenting their demographic characteristics and clinical training background, and a second questionnaire documenting their clinical strengths and preferred clinical practices. (2) When treating study cases, therapists will complete and submit the CASH-AA fidelity checklist and, for those in the Integrated condition, the MIP fidelity checklist after every session; and each condition will complete a brief checklist of evidence-based practices for adolescent behavior problems; all checklists (total completion time: 5 minutes) will be collected by research staff on a regular basis. (3) When treating study cases, therapists will audiorecord every session with consenting clients and submit the recordings to research staff on a regular basis. (4) Upon closing a study case, therapists will complete a termination summary of clinical activity that documents information about sessions held, participants in sessions, and treatment procedures that were the main foci of session activity.

Data Analysis

Preliminary Analyses and Refuser Analyses

All analyses will be preceded by examining distributional properties of variables, outliers, and need for using transformed variables or non-parametric tests. We will examine whether randomization successfully created equivalent study groups by conducting *t*-tests or chi-square tests on demographics and other variables; those that differ between groups will be entered as covariates in subsequent analyses. Logistic regression will examine potential biases due to failure to contact clients at follow-up on baseline characteristics, study condition, and their interactions. These analyses will determine whether the followed sample differs from the randomized sample and whether there is differential attrition by condition. Also, analyses on refuser characteristics will be conducted to inform the generalizability of the sample, as follows. Families completing the phone eligibility screening instrument will provide information on personal and family demographics. Families of eligible adolescents who refuse to participate in the baseline interview, or who participate in the baseline interview but do not complete an intake appointment at the assigned treatment site, will be asked to complete a brief study refuser

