measure. Also, phone screening data from the engaged versus non-engaged samples will be compared to test for significant differences in demographic or family characteristics.

Analytic Strategy to Account for Nesting Effects

The proposed study has a nested design: clients are nested within therapists, and therapists are nested within treatment sites. In a nested design, the application of a standard fixed effects GLM typically produces biased inferential tests because the error terms of units within each level are often correlated. We will use multilevel modeling with random effects that includes the sandwich estimator to adjust parameter estimates and standard errors for nested structure. This approach is used to analyze nested data when the goal is to examine outcome effects at the level of the individual (i.e., client), and the hierarchical structure of the data (i.e., client nesting at therapist level) is akin to a nuisance factor to be accounted for, but inference about the degree of correlation is not of interest. Also, the design is nested at the level of treatment site: therapists are nested within site. Recommendations stipulate that 10-20 sites are needed to produce stable estimates for random effects modeling. Because this study will include only four sites, we will adopt the typical alternative of modeling site as a fixed effect included as a nuisance covariate in analyses. This approach is the norm for multisite studies in behavioral sciences whenever there is a small number of participating sites. If the fixed effect of treatment site is significant for any given client outcome analysis, we will re-conduct the given analysis using a within-site approach; due to small sample size this would be considered an exploratory analysis.

Plan of Analysis for Main Outcomes: Aims 1 & 3

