LGC will proceed using Mplus version 7, as follows. First, we will test a series of growth curve models for each outcome, representing three forms of growth (no change, linear change, quadratic change), to determine the overall shape of the individual change trajectories; overall model fit will be evaluated by examining the chi-square, RMSEA, CFI, and TLI indices. Second, we will test unconditional models for all outcomes to obtain the average effect for change over time in outcome, without including treatment condition or other covariates. Third, we will add the two predictors, Condition (Behavioral Only vs. Integrated) and baseline Substance Use (SU+ vs. SU-) to the models in order to test the impact of each predictor on initial status and change over time. We will also test Condition X SU interactions, and if any are significant for a given outcome, we will re-run that model separately for the SU+ and SU- participants to test simple effects. Treatment effects (Aim 1) for any given outcome will be shown by a statistically significant effect parameter, as tested by the pseudo z test—calculated by dividing the coefficient by its standard error—associated with Condition. Heterogeneity of Treatment Effects (HTE; Aim 3) for any given outcome will be identified by a significant effect for the Condition X SU interaction term; post-hoc analyses will be used to explore these interactions to determine whether Integrated effects appeared to be stronger or weaker in SU+ versus SU- cases. Initially, all models will be adjusted for nuisance covariates: sex, age, and ethnicity; family income; caregiver education level; and treatment site. We will then further explore HTE (Research Question 1) by testing for outcome differences based on age, ethnicity, and sex subgroups. Per above we will use the sandwich estimator to control for therapist nesting. Effect size estimates for significant findings in Aims 1 and 3 analyses will be calculated based on Feingold's procedures for calculating effect sizes for LGC analyses. Also, for any outcome that deviates substantially from normality—typical for delinquency and SU data—we will use two-part growth curve models, which allow for the simultaneous estimation of separate but correlated continuous and categorical LGC models. Two-part models are used when a large number of participants report the absence of the given variable (i.e., no delinquent activities or SU), resulting in highly skewed data. In two-part models, the original distribution of the outcome is separated into categorical and continuous parts, each modeled by separate but correlated growth functions. In the categorical part, a binary indicator variable is created to indicate any vs. none of the outcome in question. The continuous part models the frequency of occurrence of the outcome given any positive occurrence.

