Based on 20 years of experience engaging high-risk adolescents and their families into longitudinal research, we expect to have rates of missing assessment data on outcome variables between 10-15%. All proposed analyses involving client outcome data will be carried out in Mplus, which provides full information maximum likelihood estimation (MLE), which produces unbiased parameter estimates under the assumption that data are missing at random. Moreover,

MLE outperforms other missing data approaches, such as listwise deletion, even when MAR is not met.

Risks And Benefits

Potential Study Risks

Potential Risks for Client Participants: Research Interviews and Treatment Session Recording

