Client research interviews (phone screen, baseline interview, and 3-, 6- and 12-month follow-up interviews) will be conducted by research staff primarily in the home or site clinical offices but also in other locations upon request. Caregivers and teens will be consented and interviewed separately; caregivers will consent for themselves and for their adolescents, and adolescents will assent for themselves. Recruitment procedures, randomization procedures, and assessment measures and procedures are fully described above. Caregiver consents and assessments will be administered in the preferred language: English or Spanish. Many assessment measures have Spanish versions available from the vendor; all other measures, and all consents, will be translated by a professional translation agency using back-translation techniques that are high-standard methods in the field. Clients will be fully informed about the general treatment services to be offered—with at least some focus on attention and impulsivity problems—and about randomization procedures prior to consenting to participate, in the following manner: “You and your teen agree to enter a lottery at the counseling program. Half of families in the study will be assigned to therapists who will use research tools to educate their clients about attention problems in adolescents, and half will be assigned to therapists who will use their regular procedures to educate clients. All study families will receive the same access to

all available services at the clinic.” Research staff will give a copy of the consent/assent form (consent/assent to participate in the study; consent/assent to audiotape sessions) to caregivers and adolescents, read them aloud, and then ask family members if they have any questions, clarifications, or concerns before signing. After consenting/assenting to study participation and completing the Baseline interview, families will then be linked to services at a partnering treatment site by research staff using intensive family-based engagement strategies (also described above). Caregivers will receive \$25 in vouchers for completing the Phone Screen, and caregivers and adolescents will each receive \$40 for completing the Baseline interview, \$50 apiece for the first two follow-ups, and \$100 apiece for the final follow-up interview

Site Therapists

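### The planned attrition regression, with condition interactions, does not suit the 14–21 non-responders expected at a wave, and it cannot determine whether attrition differs by condition

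*Combined protocol and SAP*

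**What the plan says.** Under Data Analysis, Preliminary Analyses and Refuser Analyses, the plan states: "Logistic regression will examine potential biases due to failure to contact clients at follow-up on baseline characteristics, study condition, and their interactions". It then draws the conclusion: "These analyses will determine whether the followed sample differs from the randomized sample and whether there is differential attrition by condition". The section does not list the baseline characteristics or say whether they enter one joint model or one at a time. It does not say whether failure to contact is counted per wave, at 12 months or at any wave. No small-sample method is named.

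The expected amount of missing data is under Analytic Plans for Missing Data: "we expect to have rates of missing assessment data on outcome variables between 10-15" percent. The same section relies on full-information maximum likelihood under missing at random and describes no sensitivity analysis.

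The nearest thing to a covariate list is in the plan of analysis for Aims 1 and 3, where it serves the outcome models: "Initially, all models will be adjusted for nuisance covariates: sex, age, and ethnicity; family income; caregiver education level; and treatment site". Baseline substance use enters those models as a predictor.

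**The concern.** A logistic model with condition-by-covariate interactions uses up events quickly. When events are few, some combination of covariates often predicts the outcome perfectly (complete or quasi-complete separation). The affected maximum-likelihood coefficients are then infinite and their Wald tests mean nothing.

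A second problem does not depend on how the model is built. With about 70 clients per arm, a sizeable difference in attrition can easily be non-significant. If that result were taken as settling the question, an imbalance would pass without comment. The plan states no use for what the attrition analysis finds, so a baseline variable that predicts dropout and is not already in the growth models has no stated route into them.

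**Working it through.** The documents give no event count, power or precision for the attrition check, so there is no stated figure to reproduce.

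**Inputs from the documents**
- Sample size: "This parametric comparative trial will randomly assign 140 inner-city adolescents with ADHD" (Project Abstract).
- Allocation: half per condition (consent wording: "Half of families in the study will be assigned to therapists who will use research tools"), taken as 70 per arm.
- Missing outcome data: 10–15%, used as a proxy for failure to contact.
- Sites: "Because this study will include only four sites" (nesting section). The Project Abstract says three, so both counts were run.
- Urn variables: sex, three-level ethnicity, substance use.

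**Assumptions**: two-sided 0.05; non-response unrelated to the covariates; independent covariates; equal site shares; substance use 50%. Sex, ethnicity, income and education shares follow the Sample Description.

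**Step 1. Events at one wave.** 140 × 0.10 = 14; 140 × 0.15 = 21.

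**Step 2. Parameters if the growth-model covariates enter jointly.** Sex 1, age 1, ethnicity 2, income 1, education 1, site 3 = 9 baseline terms. Adding condition (1) and 9 interactions gives 19 slopes. Events per slope: 14/19 = 0.7 to 21/19 = 1.1. Adding substance use gives 10 + 1 + 10 = 21 slopes. With three sites and no substance use the count is 8 + 1 + 8 = 17. The urn variables alone give 4 + 1 + 4 = 9.

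**Step 3. Separation.** It was detected by linear programming in 1,000 simulated trials per setting. Ranges within a cell are two runs.

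| Model, each with condition interactions | 14 events | 18 events | 21 events |
|---|---|---|---|
| Growth-model covariates, 4 sites (19 slopes) | 95% | 78–81% | 65–69% |
| The same plus substance use (21 slopes) | 95% | 80% | 64% |
| Growth-model covariates, 3 sites (17 slopes) | 86% | 64% | 48% |
| Urn variables only (9 slopes) | 72% | 49% | 37% |
| Ethnicity alone | 67% | 49% | 37% |
| Sex alone | 7% | 2% | 1% |

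A separate run of the 21-slope model, with 400 trials per rate and continuous income, gave 93%, 75% and 61% at 10%, 12.5% and 15% missing. Substance use alone gave 6% at 14 events and under 1% at 21; age alone gave 0% at both. Main-effects models gave 0–15% in every set tried.

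**Step 4. A cumulative outcome.** If attrition means any of three waves missed and waves are independent (an assumption), the rate is 1 − 0.90³ = 27% to 1 − 0.85³ = 39%, or 38–54 events. Separation in the four-site, 19-slope model falls to 11% and 2%.

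**Step 5. Power of the plain arm comparison at one wave.** With p̄ the mean of p₁ and p₂,

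power = Φ{ [ |p₁ − p₂|√70 − 1.96√(2p̄(1 − p̄)) ] / √(p₁(1 − p₁) + p₂(1 − p₂)) }

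For 10% versus 20%: (0.837 − 0.990)/0.500 = −0.31, so power is 38% (Fisher exact 31%). The other cases are 14% for 10% versus 15%, 51% for 5% versus 15% (Fisher 41%) and 77% for 5% versus 20% (Fisher 72%). The smallest difference with 80% power is about 14.5–17 points, for example 2.75% versus 17.25% or 6.5% versus 23.5%.

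**Step 6. Precision of the arm difference.** Half-width = 1.96√(2p(1 − p)/70): 9.9 points at p = 10% and 11.8 points at 15%. With the cumulative outcome it is 14.7 points at 27.1% and 16.1 points at 38.6%. If 10% versus 20% per wave turned into 27.1% versus 48.8% (1 − 0.80³) through independent waves, the Step 5 formula gives z = 0.70 and power 76%. If the same clients were missed each time, the cumulative rates would equal the one-wave rates and power would stay at 38%.

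**The case against.** The strongest reply is that the over-parameterised model is a construction. The plan does not say that all interactions enter together, and the 19 or 21 slopes come from a covariate list written for another analysis. This stands. A reader might infer that the plan states a 21-parameter model; it does not. Fitted one binary or continuous covariate at a time, the interaction model can nearly always be estimated.

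The event count is open to a similar reply. The 10–15% refers to missing outcome data, is not stated to be per wave, and is only a proxy for failure to contact. A cumulative definition gives more events and largely removes the separation. This also stands.

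Three further inferences are tempting but unsupported:
- *The check would fail to run.* Under quasi-complete separation only some coefficients diverge. Dropping or penalising those terms is routine, and the arm effect can usually be estimated in a main-effects model.
- *This is the plan's only check of missing at random.* The plan does not present it as one. Regressing missingness on observed variables cannot test that assumption, because dependence on observed variables is compatible with it.
- *Predictors of attrition are absent from the outcome models.* Sex, age, ethnicity, income, education, site, condition and baseline substance use are already there, and the baseline outcome is one of the four modelled times.

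It is also fair to say that the plan nowhere announces that non-significance will be read as balance, and that low power follows from a sample of 140 and no change of model removes it. Those facts limit the consequence. They do not justify saying that the analysis determines whether attrition differs.

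**Conclusion.** The concern holds in a limited form. The attrition model is under-specified. On one natural reading (growth-model covariates, joint entry, interactions, one wave, four sites) separation would affect about 60–95% of trials. On other readings the figure runs from about 37–72% (urn variables) to under about 10% (single binary or continuous covariates, at or below the top of that range).

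The firmer part is the claim to determine differential attrition. At a single wave, a doubling from 10% to 20% would be missed about 60–70% of the time, and the difference is known only to within about 10–12 points either way. A cumulative outcome raises power only so far as misses at different waves are independent, and its interval is wider. In no form does a non-significant test show balance.

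These results rest on 70 per arm, two-sided 0.05, no clustering of attrition by therapist, and 10–15% as the failure-to-contact rate. This is a preliminary analysis with no stated decision rule, so the flaw does not in itself invalidate the main comparison. It is worth correcting because a better method is cheap.

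**What to change.** 1. Define the attrition outcome: each follow-up wave separately, with any missed wave as a secondary summary if wanted.
2. At each wave, report attrition by arm as a difference with a 95% confidence interval.
3. Examine baseline predictors in a main-effects Firth-penalised logistic model on a short pre-named list.
4. Replace determine with describe.
5. Name a short list of baseline predictors of missingness not already in the growth models, for example baseline severity in other domains. Include them as auxiliary variables in the maximum-likelihood growth models whether or not they reach significance.
6. Reconcile the three-site and four-site statements, since site drives the parameter count.

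The cost is analysis-plan wording and minor programming. The downside is that condition-by-covariate attrition patterns are described and not tested; at 14–21 events this sample could not support many such tests.

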Eligibility screening. Research staff will contact the primary caregiver of referred adolescents by phone, identify our project as being affiliated with the referral source, and explain the nature of the proposed study. Staff will then seek verbal consent from the caregiver to administer a behavioral health screening instrument. Phone screens will be conducted in English

or Spanish at the preference of the family. Families will receive a \$25 honorarium for completing phone screens. Families eligible at this initial screening, based on meeting clinical cut-score criteria for ADHD and endorsement of problems consistent with at least one co-occurring behavioral disorder, will be offered the opportunity to participate in a full baseline eligibility interview. Those who agree will be scheduled for a home-based baseline evaluation prior to enrolling in outpatient services. Non-eligible families will be offered a referral to appropriate behavioral services as requested.

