Latent growth curve modeling (LGC) will be used to examine the impact of treatment Condition on change over time in client outcomes: symptoms (ADHD, conduct problems, substance use) and QOL indicators (executive and school functioning). LGC produces estimates for the growth curves of each individual and then aggregates individual trajectories to estimate mean growth parameters (intercept and slope), characterizing the sample in terms of the average baseline value of the dependent measure (intercept) and the rate and shape of change over time (slope). Analyses will utilize a 2 (treatment condition) by 2 (baseline substance use) by 4 (time) repeated measures intent-to-treat design; missing data will be handled with robust maximum likelihood estimation (described below).

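### The Aim 1 growth models let Condition predict the pre-randomisation baseline, and the success rule does not say that only an effect on change counts

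*Combined protocol and SAP*

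**What the plan says.** The plan for Aims 1 and 3 uses latent growth curves over four waves ("assessments at baseline, 3, 6, and 12-month follow-up"). It describes the intercept as "the average baseline value of the dependent measure (intercept"), so time is zero at baseline. Condition and baseline SU are then added "to the models in order to test the impact of each predictor on initial status and change over time", and Condition x SU interactions are also tested. The decision rule reads: "Treatment effects (Aim 1) for any given outcome will be shown by a statistically significant effect parameter". The test is a pseudo z test on the parameter associated with Condition, and the rule does not say whether that parameter belongs to the intercept or to change.

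The order of events is clear from the Procedures section. Families that pass the phone screen are "scheduled for a home-based baseline evaluation prior to enrolling in outpatient services". Randomisation comes later: "Cases will be randomly assigned to study condition after completing an intake interview at the assigned site". The same paragraph allows 'nearly random' assignment at sites that allocate cases by a shared clinician rotation.

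**The concern.** Condition is allocated after baseline is measured, so it cannot affect the intercept. Under randomisation the true Condition effect on initial status is zero, and any estimate of it is chance. Because SU status is also a baseline characteristic, the same holds for Condition x SU on the intercept.

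Two things follow. First, the rule as worded could be met by a chance baseline difference. Secondly, even if only change is tested, a freely estimated baseline difference makes the Condition effect on change less precise than the same data allow. The sample is set at 140 and the documents give no power calculation, so an avoidable loss of precision deserves attention.

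The choice of growth form adds to the first problem. The plan selects no change, linear or quadratic growth for each outcome before Condition enters. If no change is selected, the intercept is the only growth parameter that Condition can predict. If quadratic is selected, Condition has two change parameters and the rule does not choose between them.

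**Working it through.** The documents give no power, target effect, SD, variance components or alpha, so there is no stated figure to reproduce.

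**Inputs from the documents**
- Total sample 140: the trial "will randomly assign 140 inner-city adolescents with ADHD to (1) CASH-AA Only or (2) CASH-AA + MIP" (Project Abstract).
- Equal arms: "Half of the participants" also receive MIP, so 140 / 2 = 70 per arm.
- Waves at 0, 3, 6 and 12 months, coded t = 0, 0.25, 0.5, 1.

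**Assumptions**
- Linear growth, complete data, no therapist clustering, two-sided 0.05 per parameter.
- Baseline variance 1; intercept variance a = 0.4 to 0.7; residual variance 1 - a; slope variance b = 0 to 0.3 SD² per year²; intercept-slope correlation -0.3, 0 or +0.3, with c the matching covariance.

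**Formula.** The covariance matrix of the estimated Condition effects on intercept and slope is (2/70) x [D + (1 - a)(Z'Z)⁻¹]. D is the random-effects covariance matrix and Z has columns 1 and t.
- Sum of t = 1.75, sum of t² = 1.3125, determinant = 4 x 1.3125 - 1.75² = 2.1875.
- Hence (Z'Z)⁻¹ has entries 0.6 (intercept), 1.829 (slope) and -0.8 (off-diagonal).
- With r the correlation between the two estimates, fixing the intercept effect at zero multiplies the slope variance by 1 - r².

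**Worked case** (a = 0.5, b = 0.1, correlation 0)
- Intercept term: 0.5 + 0.5 x 0.6 = 0.80.
- Slope term: 0.1 + 0.5 x 1.829 = 1.014.
- Covariance term: -0.5 x 0.8 = -0.40.
- r² = 0.16 / (0.80 x 1.014) = 0.197, so r = -0.44 and the variance ratio is 0.803.
- SE with free intercept: √(2/70 x 1.014) = 0.170. With the constraint: 0.170 x √0.803 = 0.153.
- Power for a 0.4 SD difference in change over 12 months, Φ(0.4/SE - 1.96): 0.65 free, 0.75 constrained.

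**Range**

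| a | b | corr. | variance ratio | power at 0.4 SD, free to constrained |
|---|---|---|---|---|
| 0.4 | 0.1 | -0.3 | 0.68 | 0.58 to 0.75 |
| 0.4 | 0 | 0 | 0.72 | 0.62 to 0.76 |
| 0.5 | 0.1 | 0 | 0.80 | 0.65 to 0.75 |
| 0.6 | 0.1 | 0 | 0.85 | 0.74 to 0.80 |
| 0.7 | 0.3 | 0 | 0.92 | 0.73 to 0.76 |
| 0.6 | 0.3 | +0.3 | 0.957 | 0.64 to 0.66 |
| 0.7 | 0.3 | +0.3 | 0.986 | 0.73 to 0.73 |

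With zero or negative correlation the ratio runs from 0.68 to 0.92. Random missingness of 12.5% at each follow-up, the midpoint of the plan's expected 10-15%, leaves that range at 0.68-0.92.

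**False positives if any significant Condition parameter counts.** Two independent tests would give 1 - 0.95² = 9.75%. Allowing for the correlation r between the tests, the linear model gives 8.9-9.7%. With a free intercept and quadratic growth, under zero or negative intercept-slope correlation, any of the three Condition parameters gives 10.1-10.9%; the linear and quadratic terms alone give 6.3-6.6%.

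**Chance imbalance.** The SE of the baseline difference is √(2/70) = 0.169 SD, so a difference above 0.2 SD in either direction has probability 24%. In the worked case, a 0.2 SD difference in the fitted intercept moves the free-intercept slope estimate by 0.2 x (-0.40/0.80) = -0.10 SD per year. Across the zero and negative correlations the shift is 0.055-0.154 SD per year in size.

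**The case against.** A reader might infer that the plan intends to count baseline differences as treatment effects, or that its Aim 1 error rate is inflated as designed. The documents do not support that. The same section introduces the growth models as a way to examine the effect of Condition on change, Hypotheses 1 and 2 speak of greater decreases and greater improvements, and the text separates initial status from change. The sentence on initial status covers both predictors, and SU may properly predict it. For Condition, the test could serve as a balance check. A careful analyst would probably test the slope, so this part is a gap in wording.

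A reader might also infer that a free intercept invalidates the slope test or throws baseline away. It does neither. A free intercept is common in growth modelling, a slope-only test holds its 5% level, and baseline remains one of the four modelled waves. The cost is efficiency.

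The size of that cost rests on variance components that the documents do not give. With a positive intercept-slope correlation it can nearly vanish. Therapist clustering, covariates and the two-part models were left out of the calculation.

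Finally, 'nearly random' assignment is a trial-specific reason to leave the intercept free, because baseline equality is less secure at those sites and a true baseline difference would then bias the constrained estimate. This objection stands as a reason for a sensitivity analysis. It does not remove the case for naming the change contrast or for using baseline efficiently in the main model.

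**Conclusion.** The point holds as a specification gap combined with an efficiency loss. The rule does not exclude a parameter that can only reflect pre-randomisation differences. Taken literally, it gives about 9-10% false positives per outcome in the linear model, an excess of roughly 4-5 percentage points that arises only if the intercept is counted. Under the more natural reading the test is valid, and the cost is precision. Constraining the intercept path would lower the variance of the Condition effect on change by roughly 8-32% under zero or negative intercept-slope correlation, and by as little as 1-5% in some cases with positive correlation. These figures are illustrative and are not bounds: they assume linear growth, 70 per arm, no clustering and assumed variance components. The direction is secure under true randomisation; the size is not known. The change is worth making because it is cheap and because the rule is also ambiguous under the no-change and quadratic forms.

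**What to change.** In the plan for Aims 1 and 3:

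- With time coded 0 at baseline, fix the regressions of the intercept factor on Condition and on Condition x SU at zero. Keep SU, site and the other covariates on the intercept.
- State that Aim 1 rests on one named change contrast, for example the model-implied 12-month Condition difference, or a joint test of the linear and quadratic Condition terms.
- Keep a Condition effect on change in the model even when the pooled data favour no change, since a flat pooled curve can hide arms that diverge.
- Apply the same rules to both parts of the two-part models.
- Report the free-intercept model as a sensitivity analysis with the same change contrast.

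The cost is a few sentences, the intercept constraints in each model and one extra run per outcome. The downside is reliance on baseline equality, which is less secure at sites using 'nearly random' assignment; the sensitivity analysis would show whether the conclusion depends on it.
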